Aim 1: Feasibility will be assessed through examination of participant recruitment, retention and engagement. Specifically, we will look at the number of participants who refuse to participate in the pilot at the time of recruitment and the reason they declined participation. Secondary impacts of interest include: medication adherence as measured by the four-item MA Questionnaire (MAQ) and change in systolic and diastolic blood pressure at 3 months.

Aim 2: To test the acceptability of a 3-month SMS-based intervention in adults with uncontrolled hypertension. One cohort of 24 participants will be recruited for the SMS intervention. Acceptability will be assessed using the systems usability scale (a validated questionnaire that measures usability reliably in small samples)¹⁸ and eliciting free comments after the survey.

At the end of this pilot project, we will have preliminary data essential for a future formal efficacy trial, to be proposed in a subsequent application to the AHRQ.

Our **first hypothesis** is that over 50% of contacted patients will respond to SMS messages and over 50% will check HBPM. This estimate is based on previous study by Bobrow and

colleagues in a similar patient population.³ Our **second hypothesis** will be that > 75% will be satisfied with the service (OK or above on the usability survey).⁹

Methods and Measures

Design

A randomized control trial of 24 non-adherent participants will be monitored and followed for 3 months; An ambulatory BP arm device will be provided to all participants with printed instructions in English or Spanish (from the American Heart Association) on how to measure BP at home (HBPM). Patients will be instructed on checking their BP at least twice a week.^{14,19} Text messages will be generated by Twilio platform, keeping a record of participants contacted, sent and received texts. Participants in the control arm will receive standard of care education for controlling high blood pressure in clinic by their healthcare providers. They will be followed to monitor any changes in their BP throughout the duration of the study.

Study team members will identify patients with uncontrolled hypertension during clinic visits. Study team members will approach patients 18 years or older who have uncontrolled HTN (SBP>130 or DBP >80) and have 2 or more BP medication(s) on their medication list.

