Participants will be interviewed by the study team and those with a MAQ score of 1 to 4 will be classified as non-adherent will be invited to participate. The study team member will assess the potential participant's phone ownership, text messaging ability, text messaging willingness, and receptivity to the intervention (and record all this information). The MAQ cut-off was chosen for the study because it has been used in the literature in previous studies,²⁰⁻²² and the cut-off at this value provides a highly sensitive tool for identifying medication non-adherence.^{22,23}

Participants will be randomized into one of two groups: intervention SMS arm or the control arm. If enrolled in the intervention arm, the subjects will be contacted by phone via SMS and phone call. To ensure equal access to participation among women and minorities we will translate all materials and questions to Spanish. The privacy of potential subjects during recruitment will be protected by collecting only necessary identifiers and using a private room during the interview process.

As part of routine care, patients who present to the office with uncontrolled HTN receive instructions from their clinician on medication changes and are advised to return for a nurse visit in 2 weeks and a clinician visit in 3 months. During follow-up, the nurse checks the patient's blood pressure and contacts the clinician for further management if the BP is not controlled. Participants in the SMS arm will receive SMS messages to monitor their blood pressure in addition to this routine care whereas the control arm will only receive the standard provider education and monitoring for controlling blood pressure.

Baseline demographic characteristics of the participants will be collected. Participants will be followed with office (or phone if they no show for their visit) interviews at 2 weeks or 3 months to complete 2 validated scales: the MAQ, and SUS+ free comments

Study intervention participants will be provided with a blood pressure monitor to be used for measurement and extraction of HBPM information. Clinicians will be alerted through an in-basket message in the electronic medical record (Wake One) if the participants report BP outside the threshold range, and the patient will be sent an SMS and prompted to contact their clinic. The threshold range set for SBP is between 90 and 180 mm Hg and between 60 and 110 mm Hg for DBP for one-time measurements. These thresholds are made based on the

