recommendations by HTN guidelines, which designate a hypertensive urgency to be 180/110 mm Hg or higher and hypotension 90/60 or lower.²

Patients who no show to the follow up visits will be telephoned to assess adherence barriers. The study team member will create a telephone encounter in the electronic health record to document their discussion and route it to the patient's PCP. Patients who refuse participation in the study will be asked for the reason and their responses will be recorded to determine any barriers to participation. Study team members will attempt to contact patients who miss follow up visits every week up to 3 times, if after the 3rd time the patient is still not able to be reached, the patient will be lost to follow up.

Setting

The study team will recruit patients who fall within the eligibility criteria from Wake Forest Baptist Medical Center.

Subjects selection criteria

Eligibility and recruitment

Inclusion criteria

Patients 18 years and older who have SBP>130 or DBP >80 during an office visit encounter in the past 6 months and have BP medication(s) on their medication list.

- Own a phone with SMS capability
- Non-adherent-MAQ score of 1 to 4
- Vulnerable population (Black, Hispanic or education level < or equal high school (as an indicator of low SES)

Exclusion Criteria

- End-stage renal disease (on hemodialysis or peritoneal dialysis)
- Kidney transplant recipients
- Unable to afford BP medications or lack transportation to clinic visits
- Hospice or nursing home care
- Dementia or cognitive impairment on the problem list

Sample Size

24 patients –We will randomize 12 patients into 2 groups

Interventions and Interactions

Pilot randomized controlled study.

Participants in the SMS intervention arm will receive usual care and SMS texting and phone calls. Study team members will send secure SMS messages to participants weekly for four weeks and then every other week until their next appointment.

The secure messaging system will be as follows

Introductory message:

Welcome to managing your blood pressure with the Nephrology/ Internal medicine clinics at Wake Forest. Try to take your BP meds at the same time every day to keep your BP under control! Make it part of your daily routine:

First week

Adherence checkpoint:

1. *Good morning! Did you take your blood pressure medications today?*

“No” Response:

1. *Let's try to stay on top of taking them daily! You can do this!*

Additional prompts:

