Did you fill your prescription?

- -If no -> phone call to determine barrier to filling BP meds “Mr./Mrs. (X). My name is (Y), we met when you were in the 7th Janeway clinic. I am calling you to find out if you are having difficulties filling your prescriptions. I will let Dr. (Name) know. Have you tried our pharmacy?” Message clinician in Wake One.
- If yes
- *Did you have any side effects from your blood pressure medication?*
- -If yes -> phone call to determine side effects
- Mr./Mrs. (X). My name is (Y), we met when you were in the 7th Janeway clinic. I am calling you to find out if you are having side effects from your blood pressure medications. I will let Dr. (Name) know. Message clinician in Wake One.
- - If No, no action

“Yes” Response:

1. *Keep it up! Plus thumbs up emoji*

Self-monitoring phase:

1. *Have you been checking your BP? We'll be checking in tomorrow for results!*

“Yes” Response:

1. *Nice work!*

Additionally:

What was the top number (SBP)?

What was the bottom number (DBP)?

“No” Response:

1. *Never too late to start! Try checking your BP in the AM and PM every day for the next few days and we'll check back again later.*

Data Response/Gamification:

1. *BP measurements received. You're doing great! Keep it up – you're currently in X place among texters.*

An adapted version of the System Usability Scale (SUS) by Bangor⁹ will be administered either in person or the phone after the follow up clinic visit or at the end of week 12 (if patient misses follow up appointment).

Study team members will perform the following tasks to track study participants progress:

Protocol version: 4.30.2020

1. Weekly tracking of number of patients contacted and who responded to SMS, number of SMS questions answered, and number of office visits completed
2. Monthly tracking of patient satisfaction surveys
3. Monthly reports distributed via email to the team providing ongoing feedback on performance related to patient outreach and patient satisfaction
4. When high or low BP is reported SBP > 180 or <90 and or DBP > 110 or <60, a study team member will send a message in Wake One to the clinic triage nurses. The triage nurse will contact the patient to arrange a clinician office visit or a nurse blood pressure check appointment based on additional information on clinical symptoms.

Outcome Measure(s)

A- Feasibility

Feasibility will be assessed consistent with the recommendations of Leon and colleagues.²⁴

Specifically, we will examine:

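### The out-of-range BP alert waits for the participant's report, yet no displayed message gives the limits or says what to do with such a reading between prompts

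*Combined protocol and SAP*

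**What the plan says.** All references are to the combined protocol and SAP.

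- **Trigger.** Under Methods and Measures, Design, clinicians receive an in-basket alert "if the participants report BP outside the threshold range, and the patient will be sent an SMS and prompted to contact their clinic". Item 4 of the progress-tracking list under Interventions and Interactions has the same trigger: "When high or low BP is reported", a team member messages the triage nurses. No other trigger is described.
- **Limits.** Design sets SBP 90 to 180 mm Hg and DBP "between 60 and 110 mm Hg for DBP for one-time measurements", so one reading is enough.
- **Home checking.** Design: "Patients will be instructed on checking their BP at least twice a week".
- **Message schedule.** Interventions and Interactions: "Study team members will send secure SMS messages to participants weekly for four weeks and then every other week until their next appointment".
- **Message content.** After the greeting, the welcome text is about taking medication: "Try to take your BP meds at the same time every day to keep your BP under control". The BP prompt asks for one systolic and one diastolic value (its first question begins "What was the top number (SBP"). The limits appear only as directions to staff.
- **Routine care.** Patients with uncontrolled hypertension "are advised to return for a nurse visit in 2 weeks and a clinician visit in 3 months".

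**The concern.** The investigators chose limits at which one reading should reach a clinician or triage nurse, and they tied them to guideline definitions of hypertensive urgency and hypotension. The step works only if the participant sends the value. The text telling the participant to contact the clinic comes after that report, so it cannot be what prompts the report. Someone guided only by the displayed messages has no stated reason to act on a reading of, say, 190 mm Hg until asked for numbers.

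The longest gaps between prompts come after week 4. Routine care lists no visit between the 2-week nurse check and the 3-month clinician visit, so the fortnightly phase falls where no routine visit is stated. What is at stake is the timeliness of a safety step in participants enrolled for uncontrolled BP and poor adherence. It is not the validity of a comparison: BP change at 3 months uses office readings from the medical record.

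**Working it through.** The plan gives no figure for the delay, so there is none to reproduce. The check sets the texts side by side and counts intervals.

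**Inputs from the document**
- Follow-up: 3 months, taken as 12 weeks (Design; the secondary measures also use 12 weeks).
- Messages: weekly for 4 weeks, then every 2 weeks (Interventions and Interactions).
- Home checks: at least 2 per week (Design).
- SMS arm: 12 participants (Sample Size).

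**Assumptions**
- The messages end at the 3-month visit. If the next appointment were the 2-week nurse visit, messages would stop before the four weekly ones were complete and the fortnightly phase could not occur.
- The BP prompt is reused in later weeks. Only a first-week script is displayed.
- The participant waits for the prompt, and readings are spread evenly between prompts.

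**Step 1: prompts.** 4 weekly + 8/2 fortnightly = 8 over 12 weeks. With the first at the end of week 1, they fall on days 7, 14, 21, 28, 42, 56, 70 and 84.

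**Step 2: wait to the next prompt.** The maximum is the interval and the mean is half of it.

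| Period | Interval | Maximum wait | Mean wait |
|---|---|---|---|
| Weeks 1–4 | 7 days | 7 days | 7/2 = 3.5 days |
| Weeks 5–12 | 14 days | 14 days | 14/2 = 7 days |
| All 12 weeks, if messages are weekly | 7 days | 7 days | 3.5 days |

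The last row is there because the engagement item under Feasibility refers to 12 SMS, which could mean one message a week. These figures are approximate, since the self-monitoring text announces a check for results the next day and one contact may span two days.

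**Step 3: readings taken against readings asked for, weeks 5–12.** Instructed readings per participant: 2 × 8 = 16. Prompts: 8/2 = 4. With one pair of values per prompt, 4/16 = 25% are asked for. If a two-day contact collects two pairs, 8/16 = 50%. Either way, many readings fall between prompts. Asking for fewer readings than are taken is not in itself an error. It matters here only because nothing displayed tells the participant which readings should not wait.

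**Step 4: the displayed messages.** The welcome text, the adherence check, the prescription and side-effect prompts, the self-monitoring prompt, the two BP questions and the replies were read in turn. None states the limits, and none says to text or call about an extreme value before the next prompt.

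**The case against.** The strongest reply is that absence from the displayed messages is weak evidence of absence from the trial.

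- **Incomplete script.** Design promises an SMS to participants who report an out-of-range value, and its wording appears nowhere. Only a first-week script is displayed. This stands, and it limits the point to the displayed messages.
- **Unseen material.** Participants receive a printed leaflet with the device and sign a consent form. The protocol describes the leaflet only as explaining home measurement, so its content is unknown either way. A reader might infer that participants get no safety instruction at all. The documents do not support that.
- **Two-way channel.** The Informed Consent section says SMS-arm participants use their phones to communicate with the coordinator, and neither alert sentence restricts reports to prompted ones. This stands. What remains is that no displayed message invites an unprompted report.
- **Extraction from the monitor.** Design mentions extracting home BP information from the device. No transmission or review of device readings is linked to the alert, but a second source of values cannot be ruled out.
- **Fourteen days is a worst case.** It needs a participant who neither texts, calls nor seeks care. Someone who says they have not been checking is promised a later check-back, which may shorten the gap. Accepted.

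A reader might also try to count delayed readings. Full checking gives 12 × 2 × 8 = 192 readings in weeks 5–12. At an assumed 1% to 5% out of range, that is 192 × 0.01 = 1.9 to 192 × 0.05 = 9.6. Those rates are not in the documents, and the plan itself hypothesises only that more than half of participants will check at home. The count is an illustration and not an estimate of harm.

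**Conclusion.** The point holds in a limited form. As displayed, the messaging plan can delay an alert that the investigators meant one reading to trigger: by up to about 14 days after week 4, or up to 7 days if messages are weekly throughout. This rests on the participant waiting for the prompt, on the BP prompt continuing in later weeks, and on the unseen leaflet and consent form not already covering it.

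The documents do not show that any reading would be missed or any participant harmed, and they give no frequency for such readings. It would also be wrong to infer a bias in the results. The 3-month BP change comes from office measurements, and no sample-size or error-rate figure changes. This is a low-priority safety improvement, worth making because it costs so little.

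**What to change.** Add one instruction to the welcome text, in English and Spanish: if the top number is above 180 or below 90, or the bottom number is above 110 or below 60, contact the clinic and text us the numbers without waiting for the next message. These are the protocol's own limits and its own action, moved to before the report.

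Check the leaflet and consent form first and keep the wording consistent with them. If they already say this, the welcome text need only repeat it. The investigators should decide how urgent the wording is and whether to say anything about how texts are monitored, since the protocol states neither.

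Leave the SBP/DBP prompt unchanged. Asking for the highest and lowest values since the last message would turn two numbers into four, break the pairing of systolic with diastolic, and add burden where response is itself a feasibility outcome.

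The cost is a few words of script in two languages, a slightly longer message, and possibly a few more triage calls among 12 participants. One limit remains: Design also says the device goes to all participants, and a welcome SMS would not reach the control arm. If controls do receive monitors, the printed sheet is the place to reach them.

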Our pilot will evaluate the feasibility of implementing an SMS system and HBPM at Wake Forest Baptist Health. Implementing a new text messaging service will improve the health delivery system in three ways. 1) Increasing patient engagement: SMS and HBPM requires the patients to be highly involved and committed to improving their health and results in a marked improvement in the adherence to medication. BP measurements has also been reported to improve BP control. 2) Supporting patients outside of the office visits by identifying and resolving barriers to medication adherence earlier on (i.e. if patients are unable to get their prescriptions or are having significant side effects). 3) Adopting clinical guidelines to improve BP control in a vulnerable population.

Specific Aims

Given the high prevalence of uncontrolled hypertension (HTN), testing novel interventions that support the implementation of hypertension guidelines may improve access, quality, and health outcomes. Although mobile health and text messaging shows promise in other health promotion settings, the best strategy to support HTN management in minority non-adherent patients is still unknown.^{13,14} Thus, the goal of this pilot is to test a patient centric SMS-based text message intervention and ensure that it is feasible and acceptable in a sample of minority non-adherent patients with hypertension, currently seen in the internal medicine and nephrology clinics at WFBH.

Our long-term goal is to test an automated SMS intervention that can be disseminated and implemented to encourage adoption of hypertension guidelines by lowering blood pressure and incorporating home blood pressure monitoring in the care of vulnerable patients with uncontrolled hypertension.

The rationale for the proposed pilot is that evaluating an SMS system that considers patients' preferences and identifies barriers to adherence, is of critical importance in a learning health care system to transform health delivery, particularly for vulnerable populations. Minority populations are usually low adopters of mobile health tools and are most affected by uncontrolled hypertension.^{4,6,17}

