1. Screening: we will track the number of patients screened per month, the number enrolled per month, the proportion that are eligible who enroll.
2. Recruitment: number of participants who refuse to participate in the pilot at the time of recruitment and the reason why. Proportion of vulnerable patients screened but excluded because they did not own a phone with SMS capability.
3. Retention: the proportion of participants who continue to use the myHealth tool per month through three months will be tracked for the intervention.
4. Engagement: 12- SMS rate response of at least one home BP measurement. We will use 44% as our cut off based on an SMS study by Peters and colleagues²⁵.

Finally, we will monitor time needed for assessments and gather feedback on the participant burden.

B-Acceptability

Participants will complete the SUS in person on an I-Pad or over the phone. They will also be offered the opportunity to comment in their questionnaires about their experiences of taking part in the pilot. The SUS yields a single score on a scale of 0–100. A SUS score above a 68 would be considered above average. We will consider acceptable when >70 % of participants score the SUS above 68.²⁶

Secondary measures of interest

Medication adherence (MA) will be measured by administrating the four-item MAQ by the study coordinator during enrollment and at 3 months follow up visit. The MAQ was selected because it has been well-validated to identify adherence in HTN and scores have been shown to correlate well with a range of objective adherence measures.^{11,12}

SBP and DBP change at 3 months. BP will be measured during initial and follow up office visits by nurses or clinicians while patient is seated with automated arm devices according to standard office procedures. We will extract from the electronic medical record, SBP and DBP at enrollment and at 12 weeks follow up. The average change will be calculated and reported in mmHg.

No-show rate at 3 months' follow-up (f/u) clinic visits. If participants fail to come to their f/u visits within 7 days of their scheduled follow-up appointment, they will be considered as "no-shows". Our current clinic no-show rate is 30%, therefore if the study participants no-show rate is less than 30% we will consider our tool a feasible intervention.

Analytical Plan

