Results will be analyzed initially using descriptive statistics. Comparison between groups will be done using chi square tests for proportions, and t-tests for continuous variables. Regression analysis will be performed to identify independent outcome predictors. RedCap will be utilized to collect all patient data. Participant's demographics (including education level), co-morbidities, number of medications, number of blood pressure medications and BP numbers will be extracted from Wake One when available. Level of education will be confirmed verbally with each participant during consent process. Only one participant identifier will appear in the data collection forms.

The full analysis set will include participants who have responded to at least one SMS message post-randomization. Descriptive statistics will be computed for each treatment group; medians and percentiles will be reported for skewed continuous variables. For primary and secondary outcomes, descriptive statistics and 95% confidence intervals will be used to summarize the differences between groups. The secondary outcome of BP and other continuous variables will be assessed with a repeated-measures analysis using a mixed linear model approach. The Wilcoxon rank sum test will be used to compare MA between groups. Hypothesis tests will be 2-sided using the 0.05 significance level. Bonferroni-type adjustments for multiple testing will be implemented to control type I errors. Statistical analysis will be performed using SAS software (SAS Institute, Cary, NC).

Treatment assignment will be determined using blocked randomization

The primary analysis will consist of all subjects who responded with at least one BP measurement

Human Subjects Protection

Subject Recruitment Methods

Subjects will be identified when they come to an office visit and their blood pressure is not well controlled. The PI clinician (internal medicine preceptors or residents) will verbally alert the study coordinator on site of possible participants based on BP >140/90. The study team member will meet the patient in a private room in 7th Janeway, determine eligibility, and signed informed consent will be obtained from each subject. Once enrolled, the subjects will be contacted by phone via SMS and phone call. To ensure equal access to participation among women and minorities we will translate all materials and questions to Spanish. The privacy of

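### The no-show feasibility rule compares a sample stripped of patients with known cost or transport barriers, and met at an attended visit, with a clinic-wide 30%; those exclusions are also not counted

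*Combined protocol and SAP*

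**What the plan says.** - **Exclusion Criteria:** patients are excluded if "Unable to afford BP medications or lack transportation to clinic visits". No reason is given.
- **Subject Recruitment Methods:** "Subjects will be identified when they come to an office visit and their blood pressure is not well controlled".
- **Secondary measures of interest:** a participant who does not come within 7 days of the scheduled 3-month appointment is a no-show. The clinic's current rate is given as 30%, and the tool is to be considered feasible if the participants' rate is lower. The 30% is not restricted to patients who resemble the sample.
- **Objectives:** one of three ways the service should help is by "identifying and resolving barriers to medication adherence earlier on (i.e. if patients are unable to get their prescriptions", with side effects as the other example.
- **Interventions and Interactions:** an unfilled prescription triggers a "phone call to determine barrier to filling BP meds". Under Design, "Patients who no show to the follow up visits will be telephoned to assess adherence barriers".
- **Outcome Measure(s), Feasibility:** Screening tracks patients screened, patients enrolled and enrolment among the eligible. Recruitment tracks refusals with reasons and one reason for exclusion: "Proportion of vulnerable patients screened but excluded because they did not own a phone with SMS capability".

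**The concern.** A threshold taken from the whole clinic is a fair reference only if the sample would have the clinic's no-show rate without the tool. Two features of the design work against that. People known to lack transport are removed, as are those who cannot pay for their drugs, and both groups plausibly miss more visits than average. Everyone enrolled has also just kept an appointment. A rate under 30% could then come from selection and be credited to the tool.

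The same exclusion bears on what the pilot can say about uptake. Cost is an obvious reason for an unfilled prescription, and low education is used as an entry marker of low socioeconomic status, so the criterion removes part of the target group. Exclusions for lack of a phone are treated as a feasibility result; exclusions for cost or transport are not. The pilot is meant to inform a later efficacy trial, and a recruitment loss that was never counted would carry forward into its planning.

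**Working it through.** **Inputs from the documents.** Clinic no-show rate 30%; rule: observed rate below 30%; 24 participants, read as 12 per arm (2 × 12 = 24). The rule speaks of study participants without naming an arm, so both n = 12 and n = 24 are shown.

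**Inputs assumed.** Share of clinic patients with a cost or transport barrier, s = 10% to 20%; their no-show rate, r = 50% to 60%. The documents give neither.

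**Step 1: what the rule requires.** With n = 12, at most 3 no-shows (3/12 = 25.0%; 4/12 = 33.3% fails). With n = 24, at most 7 (7/24 = 29.2%; 8/24 = 33.3% fails).

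**Step 2: baseline with no selection and no tool effect.** At a true rate of 0.30, P(X ≤ 3 | n = 12) = 0.49 and P(X ≤ 7 | n = 24) = 0.56. The rule is thus already met about half the time by an ineffective tool. That is a weakness of a point-estimate rule in a small sample, separate from this point.

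**Step 3: rate among those who remain.** The clinic's 30% is a mixture, 0.30 = s·r + (1 − s)·q, so q = (0.30 − s·r)/(1 − s).
- s = 0.10, r = 0.50: (0.30 − 0.05)/0.90 = 0.278
- s = 0.20, r = 0.60: (0.30 − 0.12)/0.80 = 0.225

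**Step 4: chance that an ineffective tool meets the rule.**

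| True rate | n = 12 | n = 24 |
|---|---|---|
| 0.300 (no selection) | 0.49 | 0.56 |
| 0.278 | 0.56 | 0.66 |
| 0.225 | 0.72 | 0.85 |

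The exclusion therefore adds about 0.07 to 0.23 with 12 participants, and about 0.09 to 0.28 with 24.

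**Step 5: sensitivity.** With s = 5% and r = 40%, q = (0.30 − 0.02)/0.95 = 0.295, almost no shift (0.51 and 0.59). With s = 30% and r = 60%, q = (0.30 − 0.18)/0.70 = 0.171 (0.86 and 0.96).

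**Step 6: recruitment at an attended visit, taken alone.** If no-show risk varies between patients with mean m = 0.30 and intraclass correlation ICC, the expected rate among attenders is m(1 − ICC): 0.27, 0.24 and 0.21 for an assumed ICC of 0.1, 0.2 and 0.3. This overlaps with Step 3, because people without transport are less likely to be present to be screened. The two shifts should not be added.

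**Step 7: what the recruitment figures would show.** Assume 40 eligible and 24 enrolled. Enrolment among the eligible is 24/40 = 60%, however many were excluded for cost or transport. If those patients are a share e of the otherwise eligible, enrolment over eligible plus excluded is 0.60 × (1 − e): 54%, 48%, 42% and 36% for e = 10%, 20%, 30% and 40%.

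**The case against.** The strongest reply is that the restriction is open and defensible: a 24-person pilot may reasonably confine itself to patients who can obtain their drugs and attend follow-up. That stands, and nothing here requires the criterion to change.

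There is also a concurrent control arm under the same eligibility criteria, and the Analytical Plan foresees between-group differences with 95% confidence intervals. That stands too, and it supplies the remedy; but the 30% rule as written does not use that arm.

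The shift rests on assumed inputs and could be close to nil. Selecting non-adherent patients could even push the no-show rate upward. So the direction is plausible rather than established. This does not rescue the 30%, which remains unmatched to the sample.

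A reader might infer more than the documents support:
- *That the tool exists to find the barriers it excludes.* Barrier-finding belongs to one of three stated benefits, and the text messages never ask about transport. The conflict with purpose is direct for cost only.
- *That the prescription-fill branch is tested in people who do not need it.* Participants are non-adherent by selection (MAQ 1 to 4). They can leave prescriptions unfilled for other reasons or meet cost problems later, and the side-effect branch is untouched.
- *That the plan overstates its reach.* It reports no reach measure; enrolment among the eligible is openly conditional. The total screened is tracked, so some attrition may show, but not its reason.

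**Conclusion.** The point holds as one about the no-show reference and the reporting of exclusions. The clinic-wide 30% is not matched to a sample that omits known cost and transport barriers and is recruited at an attended visit. Under the 10% to 20% and 50% to 60% assumptions, the expected rate without any tool effect is 22.5% to 27.8%, and the chance of wrongly meeting the rule rises to the values in Step 4. Only the rise over 0.49 and 0.56 is due to the exclusion. The mismatch itself can be read from the text and needs none of these figures; only its size depends on them.

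The exclusion also takes out one kind of barrier that the fill branch is meant to find, as far as it is known at screening, and leaves its frequency unreported. It does not show that the intervention is untested or the eligibility criterion wrong.

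**What to change.** - **Secondary measures of interest, no-show rate:** stop judging the SMS arm against the clinic-wide 30%. Report the SMS-minus-control difference with its 95% CI over all randomised participants; the analysis sets in the Analytical Plan are defined by SMS or BP responses, which would not suit this comparison.
- **If an external reference is kept:** recompute it from the record among patients who attended an index visit with uncontrolled BP and, where records allow, had neither barrier. Matching on attendance alone would leave the exclusion uncorrected.
- **Recruitment, item 2:** count exclusions for drug cost and for transport separately, beside phone ownership. Report enrolment also over eligible plus access-excluded patients.
- **Conclusion:** limit the feasibility statement to patients without these barriers at entry.

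Eligibility, intervention and sample size stay as they are. The cost is two screening-log fields, one record query if the external reference is kept, and a less favourable feasibility statement. The interval will be wide: with 12 per arm and 30% in both, the standard error is √(2 × 0.3 × 0.7/12) = 0.187, so the 95% limits lie about 37 percentage points either side. The comparison would therefore be descriptive.
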